8.3 Concomitant Medications and Concomitant Non-drug Therapies

Concomitant treatment with systemic corticosteroids or immunosuppressants is not permitted, but co-administration of any other drugs that have no effect on the efficacy assessment is allowed. If there is a concomitant medication, the name of the drug's active ingredient (name of the product in case of a combination drug), dosage, starting/ending date of administration, and the reasons for administration are to be recorded on the case report form (CRF). Information on any concurrent therapies (ex: physiotherapy) are also required to be documented on the CRF (type, duration, etc.). All concomitant medications and therapies are to be recorded at baseline and during the trial.

The following drugs are not permitted: glucosamine, dietary supplements used as alternative medicine to treat osteoarthritis such as chondroitin sulfate and hyaluronan, systemically administered corticosteroids (Hydrocortisone, Prednisone, Prednisolone, Methylprednisolone, Triamcinolone, Dexamethasone, Paramethasone, Betamethasone, Aldosterone, Fludrocortisone) and immunosuppresant (Prednisone, Vincristine, Azathioprine, γ - globulin, Cyclophosphamide, Chlorambucil, 6-mercaptopurine, Cyclophosphamide + factor XIII, Rh(D) immune globulin, ALG, Actinomycin-D, OKT3, Methotrexate

8.4 Observation and Evaluation Items

8.4.1 Demographic Background and Medical History of Subjects

The patients will be screened by survey of demographic background and medical history to determine their eligibility for enrollment.

✓ Demographic background: the patient's initials, date of birth, age, gender, body weight, height, ethnicity, etc.

- ✓ Medical history: the patient's current or past diseases of substantial significance
- ✓ Vital Signs and Physical Examination: vital signs will be monitored and recorded at screening, after administration of the investigational product, and at each follow-up visit.
- ✓ Vital signs: blood pressure, pulse

✓ Physical examinations: general condition, nutritional condition, skin/mucosa, eye, ENT, thyroids, lungs, cardiovascular system, abdomen, kidney, spine/extremities,

CONFIDENTIAL: These all contents herein are the sole property of MEDIPOST Co., Ltd. Any reproduction or distribution of this document without the written consent of MEDIPOST Co., Ltd is prohibited. Copyright © 2014 MEDIPOST Co., Ltd.

peripheral circulation, neuro-psychiatric system, lymphatic system, etc

8.4.2 Concomitant Medications

Each participating subject must be inquired at baseline and throughout the treatment period and at each follow up visit whether he or she is on any concomitant medications. And detailed information of the medication such as the name of the drug's active ingredients (name of the product for a combination drug), dosage, start and end dates of the administration, and a reason for the administration should be documented on case report form.

8.4.3 Evaluation of Adverse Events & Toxicity

Any adverse events (AE) or toxic reactions of each participating subject will be evaluated throughout the course of the study and at each follow up visit (from Day -2 to the end-of-study visit). Any adverse events or serious adverse events will be managed, investigated, and reported according to the procedures described in the following sections:

✓ Adverse Events

When an adverse event is either observed by the investigator or reported by a subject, the investigator, regardless of the relationship of the AE to the investigational product, will record name and type of the adverse event, the severity, dates of onset and resolution of the event, the investigator's opinion on the relationship between the investigational product and the adverse event, and whether or not the event was an SAE (serious adverse event) on the case report form (CRF).

The principal investigator or the trial coordinator will carry out follow-up observations for all subjects with adverse events until the symptoms subside and the abnormal clinical test results are returned to normal, or until a satisfactory explanation can be given for the observed changes. If and when there is such a request from the sponsor, a progress report on the adverse event will be submitted to the trial coordinator.

✓ Serious Adverse Events

A serious adverse event is defined as any untoward medical occurrence at any dose that causes death, life-threatening condition, in-patient hospitalization or prolongation of existing hospitalization, persistent or significant disability/incapacity, a congenital anomaly/birth defect, or another important medical event (see below).

CARTISTEM®

CONFIDENTIAL: These all contents herein are the sole property of MEDIPOST Co., Ltd. Any reproduction or distribution of this document without the written consent of MEDIPOST Co., Ltd is prohibited. Copyright © 2017 MEDIPOST Co., Ltd

Important medical events that do not result in death, are not life-threatening, or do not require hospitalization may be considered SAEs when, based on appropriate medical judgment, they may jeopardize the subject and may require medical or surgical intervention to prevent one of the outcomes listed above. Examples of such medical events include allergic bronchospasm requiring intensive treatment in an emergency room or at home, blood dyscrasias or convulsions that do not result in in-patient hospitalization, or development of drug dependency or drug abuse. If a serious adverse event occurs, the investigator must, regardless of the relationship of the SAE to the investigational product/treatment, report the event to the responsible Institutional Review Board/Independent Ethics Committee and to the sponsor within 24 hours of awareness of the event by the investigator or, at the latest, by the next working day.

If an unexpected fatal or life-threatening adverse event occurs, the sponsor must report to the FDA by telephone or fax within seven days and report in writing of unexpected and serious adverse events within 15 days as required under 21CFR312.32.

8.4.4 Laboratory Evaluations

Laboratory evaluations will be performed at screening, after final administration of the investigational product and at every follow-up visit.

1) Hematology: Hematocrit, Hemoglobin, MCV, MCH, MCHC, RBC, WBC, Platelet, Differential count (Neutro, Eosino, Baso, Lympho, Mono)

2) Blood Chemistry: GOT(AST), GPT(ALT), Alkaline Phosphatase, Glucose, Urea(BUN), Creatinine, Direct bilirubin, CK, LDH, Uric acid, Albumin, Total Protein

3) Blood coagulation test: PT, aPTT

4) Electrolytes: Sodium, Potassium, Chloride

5) Urinalysis: Color, Specific gravity, pH, Leucocytes, Nitrite, Protein, Glucose, Ketone, Urobilinogen, Bilirubin, RBC, Microscopy

8.4.5 Immunogenicity study

T cell subset for immunogenicity evaluations will be performed at Screening, at 24week 12-month, and 24-month visit.

8.4.6 IKDC Score

page 38 of 137

CONFIDENTIAL: These all contents herein are the sole property of MEDIPOST Co., Ltd. Any reproduction or distribution of this document without the written consent of MEDIPOST Co., Ltd is prohibited. Copyright © 2017 MEDIPOST Co., Ltd

The subjects will undergo a self-assessment of knee function using IKDC subjective knee evaluation score before and after the drug administration in order to determine the efficacy of the investigational product. The IKDC assessment will be performed at the 4, 8, 12, 24 weeks and 12 and 24 months after the drug treatment in an exploratory fashion but the IKDC score from the 12 month time point will be used as a primary result of the post-operative change.

8.4.7100-mm VAS Evaluation

The subjects will undergo a self-assessment of joint pain using 100 mm VAS before and the 2, 4, 8, 12, 24 weeks and 12 and 24 months after the drug administration for the efficacy evaluation. Use of NSAIDs must be discontinued for 6 weeks prior to treatment and may be resumed following the treatment. Use of NSAIDs and any other analgesics must be discontinued for 48 hours and 24 hours, respectively, prior to VAS evaluation at Weeks 4, 8, 12, and 24, and Months 12 and 24. Patient may be allowed to take analgesics within 24 hours prior to VAS evaluation at Week 2.

8.4.8 Lysholm Score

The subjects will undergo a self-assessment of knee function using Lysholm Score before and the 4, 8, 12, 24 weeks and 12 and 24 months after the drug administration for the efficacy evaluation.

8.4.9 KOOS Score

The subjects will undergo a self-assessment of knee function and knee-related qualityof-life (QoL) using KOOS Score before and the 4, 8, 12, 24 weeks and 12 and 24 months after the drug administration for the efficacy evaluation.

8.4.10 MRI Assessment

Structural information will be gained using high-resolution (1.5 or 3 Tesla) magnetic resonance imaging (MRI) at Screening, week 24, month 12, and month 24 in order to evaluate the clinical symptom improvement. The MRI evaluations at week 24, month 12 and month 24 will also evaluate for tumorigenicity at focal lesion.

8.5 Early Discontinuation from the Study

Drop-out or withdrawal of a subject from the study can be determined at any time point during the study period by reporting to the trial coordinator or the principal investigator.
CARTISTEM® page 39 of 137

CONFIDENTIAL: These all contents herein are the sole property of MEDIPOST Co., Ltd. Any reproduction or distribution of this document without the written consent of MEDIPOST Co., Ltd is prohibited. Copyright © 2017 MEDIPOST Co., Ltd

Should a patient voluntarily decide to withdraw, the decision will be respected and accepted without any questions.

Purpose of this study is to evaluate the safety and the efficacy of the investigational product. Therefore, any subjects who want to withdraw from the study on a voluntary basis or due to the adverse events will be replaced with new subjects as long as the drug administration in the dosage group that the withdrawn subject was in is not complete. The study data obtained from such a subject until the point of drop out will be, where possible, included in the data pool for analysis at the final evaluation stage.

9 Definition of Adverse Events

An adverse event (AE) is defined as any undesired clinical responses or complication experienced by a subject. All operative and postoperative adverse events, whether related or not, will be documented on the AE case report form (CRF).

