CARTISTEM® PHASE I/IIa CLINICAL TRIAL PROTOCOL MP-0201-01

Version 3.2 Date: 15 March, 2017

CARTISTEM® PHASE I/IIa CLINICAL TRIAL PROTOCOL

CARTISTEM®

page 1 of 137

CONFIDENTIAL: These all contents herein are the sole property of MEDIPOST Co., Ltd. Any reproduction or distribution of this document without the written consent of MEDIPOST Co., Ltd is prohibited. Copyright © 2017 MEDIPOST Co., Ltd.

Name of Company Name of Product: Umbilical Cord Blo Ex vivo, Combined	Protocol #: MP-0201-01								
Protocol Title	Evaluation of Safety and Exploratory Efficacy of CARTISTEM [®] , a Cell Therapy Product for Articular Cartilage Defects: A Phase I/IIa Clinical Trial in Patients with Focal, Full-thickness Grade 3-4 Articular Cartilage Defects of the Knee								
Clinical Phase	Phase I/IIa								
Study Overview	dy Overview CARTISTEM [®] will be administered at doses ranging from 0.5×10 ⁷ to 2.25×10 ⁷ hUCB-MSC (0.25×10 ⁷ cells/cm ² ; 0.5 mL/cm ² with 0.5×10 ⁷ MSC/mL) to patients with focal, full-thickness, Grade 3-4 articular cartilage defects of ≥ 2cm ² in size. Safety: Patient safety will be assessed step-wise with increasing levels of total hUCB-MSC and HA exposure: a total of 12 patients will be enrolled and treated with CARTISTEM [®] to evaluate whether dose limiting toxicity (DLT) is detected. DLT is defined as toxicity or adverse event of Grade 3 or higher [80 points or higher for pain] in two or more events at the surgery site among swelling, tenderness, range of motion, and pain in any one visit. DLT is also defined as adverse drug reaction of Grade 3 or higher in the Common Toxicity Criteria Adverse Events (CTCAE), Version 4.0, with the exception of the following events and that they are unresolved for 7 consecutive days, despite medical interventions: ✓ Abnormal results in lab test (Acidosis, Hyponatremia, Hyperbilirubinemia, etc.) ✓ Abnormal results in lab test (Acidosis, Hyponatremia, Hyperbilirubinemia, etc.) ✓ Pain, defined as severe pain; limiting self-care ADL ✓ Pain, defined as severe pain; limiting self-care ADL								
	✓ Fever, defined as > 40.0 degrees C (> 104.0 d	degrees F) for > 24 hours							
	Initially, 6 patients with lesion sizes of 2-5 cm ² w (Dosage A); if dose limiting toxicity is not detect after administration, an additional 6 patients, with	ed during a 12 week period							

page 2 of 137

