4.3 CARTISTEM[®] (MEDIPOST Cell Therapy Product)

CARTISTEM[®] is intended to be used as a single-dose cellular therapeutic agent for cartilage regeneration in human subjects with cartilage defects of the knee as a result of ageing, trauma or

CONFIDENTIAL: These all contents herein are the sole property of MEDIPOST Co., Ltd. Any reproduction or distribution of this document without the written consent of MEDIPOST Co., Ltd is prohibited. Copyright © 2017 MEDIPOST Co., Ltd.

degenerative diseases.

The CARTISTEM[®] drug product consists of a combination of human umbilical cord bloodderived mesenchymal stem cells (hUCB-MSC; supplied as a liquid suspension) and lyophilized sodium hyaluronate, provided in separate vials for mixing prior to administration. The packaged drug product will be shipped and stored as two vials, one vial containing approximately 7.5x10⁶ hUCB-MSCs suspended in 1.5 mL medium (alpha-MEM) to be mixed with one vial containing 60 mg sodium hyaluronate (lyophilized). Upon admixture of the two vials, i.e. after distribution of the cells in the hyaluronate polymer, the reconstituted product (5x10⁶ cells/mL; 40 mg/mL sodium hyaluronate) is formed as a viscous gel which is implanted into the cartilage lesion during open surgery. The initial proposed clinical dose is to be 0.5 mL/cm² (approximately 2.5x10⁶ cells and 20 mg HA/cm²). Immune phenotype tests using flow cytometer demonstrated that the hUCB-MSCs are CD45 negative, CD14 negative, HLA-DR negative, CD29 positive, CD73 positive, CD105 positive, and CD166 positive.

hUCB-MSCs, the active ingredient in CARTISTEM[®], are expected to induce the regeneration of damaged cartilage tissues by repair of the microenvironment with paracrine effects or by differentiation towards tissue-specific pathways. Sodium hyaluronate is believed to function as a medical device to provide mechanical stability to the hUCB-MSC suspension, enabling the cells to remain at the site of the implantation and not disseminate into adjacent areas.

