6.1 Study Period

- 1) 24 months from approval of the clinical trial protocol
- 2) Recruiting period: 7 months
- 3) Follow-up period: 12 months from baseline (week 0) to final visit
- 4) Long term follow-up visit: 24 months following administration of CARTISTEM®

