6.3 Number of Subjects

1) Estimated Number of Patients

This study requires 12-18 patients (6-9 patients per arm depending on rate of DLT) for two different dose ranges (Dosage A: defect sizes of 2-5 cm² and Dosage B: defect sizes of above 5 cm²).

2) Target Number of Subjects and Rationale

This is a phase I/IIa clinical trial to evaluate safety and exploratory efficacy of the investigational drug product. Therefore, it is not considered critical to base the number of subjects on formal statistical power calculations. Six patients at each dose cohort enrolled sequentially are considered sufficient for this study. This study will be performed with two dose ranges, on the basis of existing pre-clinical test results. Initially, 6 patients with defect sizes of 2-5 cm² will be enrolled in Dosage A. If no DLT is seen during Dosage A, another 6 patients with larger defect sizes (above 5 cm²) will be recruited for Dosage B of the study. There could be a need for an intermediate dose or up to 6 additional patients, based on the rate of DLT seen.

CARTISTEM®

page 21 of 137

CONFIDENTIAL: These all contents herein are the sole property of MEDIPOST Co., Ltd. Any reproduction or distribution of this document without the written consent of MEDIPOST Co., Ltd is prohibited. Copyright © 2017 MEDIPOST Co., Ltd.

1) Initial Administration Dosage and Rationale

It is somewhat well understood by developers and regulators of living cell therapies that for products like CARTISTEM[®] administered locally into an anatomical defect there is no simple extrapolation of a safe starting dose in humans based primarily upon body surface area calculations derived from animal studies.

In addition, dose determinations in this clinical setting should take into account the surface area of the cartilage defect such that all NOAEL values should be converted into a unit quantity (cells/cm²) at the application site. This approach applies to most therapeutics administered into anatomical compartments that have little subsequent distribution outside of the compartment; it is recommended that doses are normalized between species according to the compartmental volumes and amount of the therapeutic product.

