6.5 Dose Escalation

This clinical trial will employ the following dose escalation scheme:

[figure not shown]
A total of 12-18 patients will be enrolled and treated with CARTISTEM[®] for dose limiting toxicity (DLT) evaluation. Initially, 6 patients with lesion sizes of $2 - 5 \text{ cm}^2$ will be assigned to Dosage A and treated with $0.5 - 1.25 \times 10^7$ MSCs; if dose limiting toxicity is not observed at the 3 month time point for the first clinical efficacy evaluation, then another 6 patients with lesion sizes of above 5 cm² will be assigned to Dosage B and treated with more than 1.25 x 10^7 MSCs for further safety evaluation. If a DLT occurs to one or two patients of the group treated with the dosage A, 3 more patients will be assigned to dosage A. If DLT happens to 3 of the patients who were treated with the dosage A or above, this study will be halted and the FDA and IRB will be notified. The Independent Data Monitoring Committee will perform a comprehensive review of safety (see Section 9.1).

CARTISTEM®

page 24 of 137

CONFIDENTIAL: These all contents herein are the sole property of MEDIPOST Co., Ltd. Any reproduction or distribution of this document without the written consent of MEDIPOST Co., Ltd is prohibited. Copyright © 2017 MEDIPOST Co., Ltd.

If no DLT occurs to any of the dosage A patients, another 6 patients with larger defect sizes will be enrolled and assigned to dosage B. In case of no DLT observed, a total of 12 patients will be enrolled for safety and efficacy evaluation. However, 18 patients could be enrolled if DLT occurs to two patients. If DLT occur 3 or more patients treated with Dosage B, this study will be halted and the FDA and IRB will be notified. The Independent Data Monitoring Committee will perform a comprehensive review of safety (see Section 9.1).

CARTISTEM®

page 25 of 137

CONFIDENTIAL: These all contents herein are the sole property of MEDIPOST Co., Ltd. Any reproduction or distribution of this document without the written consent of MEDIPOST Co., Ltd is prohibited. Copyright © 2017 MEDIPOST Co., Ltd.

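### Replacement of withdrawn patients closes at a cohort's last implantation, before the DLT gate is judged, so the step to Dosage B can rest on fewer than six patients observed to that gate

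*Combined protocol and SAP*

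**What the plan says.** Section 8.5 covers "any subjects who want to withdraw from the study on a voluntary basis or due to the adverse events" and says that they "will be replaced with new subjects as long as the drug administration in the dosage group that the withdrawn subject was in is not complete". Its condition is completion of dosing in the group, not completion of observation. Section 4.3 describes the product as "intended to be used as a single-dose cellular therapeutic agent".

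The synopsis makes Dosage B depend on no DLT over the 12 weeks after administration. Section 6.5 words the gate as "if dose limiting toxicity is not observed at the 3 month time point for the first clinical efficacy evaluation"; when it is met, six people with larger lesions go to Dosage B. It adds three Dosage A patients only when one or two DLTs have occurred; loss to follow-up adds none.

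On cohort size, Section 6.3 states: "Six patients at each dose cohort enrolled sequentially are considered sufficient for this study". It gives a total of 12 to 18 patients, six to nine per arm, with the range driven by the DLT rate.

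Section 10.1.1 bases the safety population on all treated patients. No section defines a DLT-evaluable patient. Section 8.5 keeps a withdrawn patient's data for the final evaluation, where possible, but is silent on how that patient counts at the escalation decision. Appendix 5 requires a DSMB meeting before Dosage B starts and sets no minimum number observed.

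**The concern.** The natural reading is that Dosage A dosing is complete on the day its last patient is implanted. That patient then still has the whole DLT window to run, and patients implanted shortly before have most of theirs. Anyone who leaves in that interval without a recorded DLT is not replaced. Nothing in Section 6.5 prevents the step to Dosage B in that case, because its test is only whether a DLT was seen.

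Section 8.5 expressly includes withdrawal because of adverse events, so a loss may be linked to tolerability and still fall short of the DLT definition. At stake is how much evidence lies behind the move to larger defects, which receive more cells and more hyaluronate. The same gap affects Dosage B: the maximum-tolerated-dose rule in Section 6.6 counts DLTs with no evaluable denominator.

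**Working it through.** **The plan's own figure.** Two cohorts of six give 2 × 6 = 12 and two of nine give 2 × 9 = 18, which reproduces the 12 to 18 in Section 6.3. There is no power calculation to reproduce.

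**Inputs from the documents.** Six patients per cohort (6.3); one administration (4.3); a 12-week DLT window (synopsis); "Recruiting period: 7 months" (6.1).

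**Assumptions.** Even accrual, with both cohorts and the 12-week gate fitted inside the seven months; constant withdrawal and DLT hazards over 12 weeks; withdrawal of 2%, 5% or 10% per 12 weeks; true DLT rates p of 10%, 20% or 30%. The documents give none of these.

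**Step 1: how much observation falls after replacement closes.**
- Seven months = 7 × 365.25/12/7 = 30.44 weeks. Less 12 weeks for the gate, 18.44 weeks remain.
- Two cohorts of six have 10 within-cohort intervals, so each is 1.84 weeks and a cohort is dosed over 5 × 1.84 = 9.22 weeks.
- At the last implantation the six patients have 9.22, 7.38, 5.53, 3.69, 1.84 and 0 weeks observed, 27.7 in total.
- The full window is 6 × 12 = 72 patient-weeks, so 72 − 27.7 = 44.3 (62%) fall after replacement has closed.

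**Step 2: chance of at least one unreplaced withdrawal in a cohort.** This is 1 − exp(−λ × 44.3) with λ = −ln(1 − d)/12. For d = 2%, 5% and 10% it is 7%, 17% and 32%.

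**Step 3: effect of one such withdrawal.** With n patients fully observed, P(no DLT) = (1 − p)^n. Giving the leaver no observed time (n = 5) sets the upper limit.

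A leaver normally has some time observed. If t is the time already observed at closure, a leaver's mean observed time is Σ(12² − t²)/2 ÷ 44.3 = 7.6 of 12 weeks (64%). Averaging (1 − p)^(T/12) over leaving times T gives factors of 0.935, 0.869 and 0.800, which multiply (1 − p)^5.

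| True DLT rate | Six observed | Five, leaver gives nothing | Rise (points) | Five plus average leaver | Rise (points) |
|---|---|---|---|---|---|
| 10% | 53.1% | 59.0% | 5.9 | 55.2% | 2.1 |
| 20% | 26.2% | 32.8% | 6.6 | 28.5% | 2.3 |
| 30% | 11.8% | 16.8% | 5.0 | 13.4% | 1.7 |

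**Step 4: allowing for the chance that a withdrawal happens.** For each patient, the no-DLT probability is weighted by the chance of staying or leaving after closure, and the six are multiplied. Across d = 2% to 10%, P(no DLT) rises by about 0.1 to 0.9 points with credit for observed time, and by 0.4 to 2.6 points with none.

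**Precision.** The one-sided 95% upper bound on the DLT rate after zero DLTs is 1 − 0.05^(1/n): 39.3% for n = 6 and 45.1% for n = 5.

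**The case against.** The best defence is that the wording gap matters little in practice. The DSMB must meet before Dosage B, reviews individual as well as aggregate data unblinded, and would see a missing Week 12 visit among six patients. Section 9.1 adds ongoing committee review with power to recommend revising or closing the trial. Section 8.4.3 requires adverse events to be followed until they subside, though it does not say that this continues after withdrawal. A DLT recorded before a patient leaves still counts, and withdrawals before the last implantation are replaced. All of this stands and limits the consequence. None of it says how many observed patients the decision needs, and Appendix 5 leaves the guidelines and stopping rules to be established later.

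A reader might infer three stronger things that the documents do not support:
- That the plan promises six fully observed patients. Section 6.3 speaks of patients enrolled; the need for observation is inferred from the 12-week test.
- That early leavers are counted as free of DLT. Section 6.5 is silent on patients not assessed at three months. It permits that count but does not state it.
- That the gate is the only safeguard before Dosage B. The DSMB meeting is another.

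**Conclusion.** The gap is real. As written, Sections 8.5 and 6.5 allow Dosage B to open on fewer than six Dosage A patients observed to the gate, and no other section closes this. It is worth correcting, but the numerical effect is modest.

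One might read the 5 to 6.6 point rise as the cost of each withdrawal. It is a ceiling, reached only if the leaver contributes no observation. With even accrual and constant hazards the figure is about 2 points, nearer the ceiling if DLTs tend to come late. The documents give no timing of DLTs, no dropout rate and no expected DLT rate, so every percentage here is conditional on assumed values. The wording gap itself depends on none of them.

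**What to change.** Reconcile Sections 8.5, 6.3, 6.5 and 6.6:
- Define a DLT-evaluable patient as one who was treated and either had a DLT or was observed through the Week 12 visit.
- In 8.5, tie replacement to the number of DLT-evaluable patients in the group rather than to completion of dosing.
- Keep every patient with a DLT in the count, whether or not that patient withdraws, and every treated patient in the safety population.
- State how a patient who leaves before Week 12 without a DLT is treated at the escalation decision.
- Give the DSMB the evaluable denominator at its meeting before Dosage B.

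This settles who is counted. It changes no dose, DLT criterion or DLT threshold.

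The cost is an occasional extra patient and some delay. The protocol must say that replacements are allowed within or beyond the 12 to 18, because that range is now tied to the DLT rate. When a late replacement is needed, Dosage B cannot open until at least 12 weeks after that patient is implanted. Under the accrual layout above, which fills the seven months exactly, recruitment would overrun.

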10.1 Analysis Populations

10.1.1 Safety Population

The safety analysis for all clinical and laboratory adverse experiences will be based on all enrolled patients who are administered the investigational product.

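### Section 8.5 pools a leaver's data only up to drop-out and makes no provision for safety follow-up or tumorigenicity MRI after the single implant, and this is not reconciled with 8.4.3

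*Combined protocol and SAP*

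**What the plan says.** Section 8.5 is the whole discontinuation plan. A patient's wish to leave is met as follows: "Should a patient voluntarily decide to withdraw, the decision will be respected and accepted without any questions". On replacement it says that "any subjects who want to withdraw from the study on a voluntary basis or due to the adverse events will be replaced with new subjects", but only "as long as the drug administration in the dosage group that the withdrawn subject was in is not complete". On data it says: "The study data obtained from such a subject until the point of drop out will be, where possible, included in the data pool". It describes no exit assessment or later safety contact. It does not distinguish a patient who stops attending from one who withdraws consent, and it does not refer to 8.4.3.

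Section 8.4.3 evaluates adverse events from Day -2 to the end-of-study visit. It says that the principal investigator or trial coordinator "will carry out follow-up observations for all subjects with adverse events until the symptoms subside" and abnormal results normalise, or until the change is satisfactorily explained. It makes no exception for subjects who have left.

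The late safety schedule is in 8.4.10 ("The MRI evaluations at week 24, month 12 and month 24 will also evaluate for tumorigenicity at focal lesion") and in 8.4.5, which places T-cell subset tests at the same three visits. Section 10.1.1 says that the safety analysis "will be based on all enrolled patients who are administered the investigational product". Section 10.2.1 asks for a detailed description of patients who drop out because of adverse events. Section 10.2.2 gives 95% confidence intervals for the incidence of adverse events, adverse drug reactions and serious adverse events in each dose group.

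**The concern.** Safety is the primary objective, and the product is an allogeneic cell implant given once (sections 4.3, 5 and 8.1). After Day 0 no study dosing remains to stop, so a patient who leaves because of an adverse event gives up only observation. Such a patient is arguably among those whose later course matters most.

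Two kinds of information are at risk. The first is the outcome of an adverse event already present at exit: 8.4.3 has it collected, but 8.5 cuts the analysis pool at drop-out. The second is anything that first appears later, including a finding on a tumorigenicity MRI, because no section arranges for a leaver to be contacted or scanned. With 6 patients per cohort, each missing late assessment is a sizeable share of the evidence.

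**Working it through.** **Step 1. What each section provides for a treated patient who leaves.**

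| Information | Collected? | In the analysis pool? |
|---|---|---|
| Data before drop-out | Yes | Yes, where possible (8.5) |
| Course of an adverse event present at exit | Yes, to resolution or explanation (8.4.3) | Not after drop-out, on the wording of 8.5 |
| New or late adverse event | Within the 8.4.3 window to end of study, but no contact with leavers is arranged | Not after drop-out, on the wording of 8.5 |
| MRI and T-cell tests at Week 24, Month 12, Month 24 | No provision after withdrawal | Not applicable |

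A site can comply with both 8.4.3 and 8.5. They are unreconciled because one collects what the other leaves out of the analysis.

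**Step 2. Figures in the plan.** Section 6.3 sets 6 + 6 = 12 patients, or up to 18 depending on DLTs, and declines a formal power calculation. There is no drop-out rate and no precision target, so there is no stated figure to reproduce. The calculation below illustrates assumed losses.

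**Step 3. Precision when some of the 12 are not followed.** Assume that k = 1, 2 or 3 patients are lost before the later assessments and not replaced, and that no event is seen in the rest. The exact (Clopper-Pearson) two-sided 95% upper limit for 0 events in n patients is 1 − 0.025^(1/n).

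- n = 12: 1 − 0.025^(1/12) = 26.5%
- n = 11: 28.5%
- n = 10: 30.8%
- n = 9: 33.6%
- One cohort, n = 6: 45.9%; with one lost, n = 5: 52.2%

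**Step 4. Chance of seeing at least one event.** This is 1 − (1 − p)^n. At an assumed true risk of p = 10% it is 71.8% for n = 12, 68.6% for 11, 65.1% for 10 and 61.3% for 9.

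**Step 5. Bounds when leavers' outcomes are unknown.** If no event is seen in those followed, the true count among 12 lies between 0 and k: up to 1/12 = 8.3%, 2/12 = 16.7% or 3/12 = 25.0%. Within one cohort of 6, a single unknown outcome allows up to 1/6 = 16.7%.

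**Step 6. Effect of replacement.** If two leavers are replaced, 14 patients are treated and 12 followed. The limit for those followed returns to 26.5%, but the two unknown outcomes still allow up to 2/14 = 14.3%. Replacement restores the number followed, not the leavers' outcomes.

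**The case against.** Several stronger readings are tempting, and the documents do not support them.

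- **Withdrawal ends observation.** Section 8.5 never says so. It states who may leave, when they are replaced and which data are pooled. The rest is silence.
- **8.4.3 and 8.5 give opposite instructions.** They do not. The adverse event that led a patient to leave must still be followed under 8.4.3.
- **Leavers are removed from the safety analysis.** They stay in the safety population (10.1.1). Drop-outs due to adverse events are counted (synopsis) and described in detail (10.2.1), and the monitoring board sees individual safety data (Appendix 5).
- **Unobserved patients count as event-free, so the confidence intervals are too narrow.** No section scores a missing assessment as negative. The planned intervals are for adverse event, drug reaction and serious event rates, and a patient who left because of an adverse event is already in the adverse event numerator. Section 10.2 sets no denominator or interval for tumorigenicity MRI. That is a gap in reporting.

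It is also fair to say that 8.5 concerns subjects who want to leave, and that full withdrawal of consent must end data collection. The losses used above are assumed. The shift from 26.5% to 30.8% alters no decision rule, and the 12-week escalation assessment precedes every tumorigenicity MRI. The consent pages are not in the reviewed text, so an offer of continued follow-up there cannot be ruled out.

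These points limit the claim but do not close the gap. Nothing in the plan under review provides late assessments for a patient who would accept them, or brings safety data gathered after withdrawal into the analysis.

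**Conclusion.** The point holds as a missing provision. Following 8.5 as written leaves safety outcomes collected after drop-out outside the analysis pool, and makes no arrangement for the scheduled MRI and T-cell tests in treated patients who leave. The text of 8.5, 8.4.3, 8.4.5 and 8.4.10 is enough to show this.

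Its size depends on how many leave, which the documents do not say. For 1 to 3 unreplaced losses among 12 and no observed event, the upper limit moves from 26.5% to between 28.5% and 33.6%, and between 1 and 3 late events could be missed. The loss of precision is modest. The possible selection matters more, since leaving may be related to the outcome; that relation is plausible but not shown. This is a cheap improvement that serves the primary objective, not a flaw that undermines the design.

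**What to change.** In 8.5:

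1. Separate stopping study visits from withdrawing consent.
2. Ask each treated patient who wants to leave whether they agree to safety-only follow-up (adverse event contact and the already scheduled safety visits, MRI and T-cell tests to Month 24), and record the answer. Reconcile this with the present wording on accepting withdrawal without questions.
3. Cross-refer to 8.4.3, and state that safety data obtained with consent after withdrawal enter the safety analysis.

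In 10.2, report MRI and late-event findings with the number actually assessed at each time point, alongside the number treated.

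An exit visit that also collects the efficacy scores is optional; the safety argument does not depend on it.

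The cost is amendment and consent wording, plus some visits and scans for patients who would otherwise have left. Some will decline, so missing late data will be reduced but not eliminated. No dose or clinical rule changes.
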